6. STUDY DESIGN

This is a prospective, randomized, double-blind, placebo controlled multi-center Phase 2 study in up to 160 infants who meet the NICHD cooling study enrollment criteria and have cord blood collected and available for up to two infusions in the first 48 postnatal hours. We will evaluate the efficacy of the infusions of autologous umbilical cord blood. We project accrual of 60-80 subjects per year. The study will include two groups (up to 80 subjects per group), randomized to receive up to two doses of cells (with a dose range of $2-5 \times 10^7$ cells/kg per dose) or up to two doses of placebo. The randomization will be stratified by severity of encephalopathy, as defined in the NRN's Optimizing Cooling trial¹⁹. Investigators and families will be blinded to enrolled study group.

A Phase II Multi-site Study of Autologous Cord Blood Cells for Hypoxic Ischemic Encephalopathy (HIE) IND 14753 (BABYBAC II)

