In keeping with the Bayesian nature of the trial design, we will use a Bayesian interim monitoring approach to determine whether systematic differences are emergent among the two treatment groups in the incidence of any of the adverse events listed above. Specifically, after every 40 babies enrolled in the trial have spent 24 hours post their final study transfusion, we will calculate the posterior probability that one group has higher incidence of any adverse events than another. In statistical terms, the treatment will be considered harmful (i.e., the DSMC may consider termination of the trial) if for a pre-specified threshold η , the posterior probability of treatment harm (in terms of the above adverse events) is greater than η ; in other words if the predictive probability $P(\theta > 1 | X) > \eta$, where θ denotes the relative risk favoring the treatment group and X is the data available. In order to allow for a liberal safety monitoring regime to ensure patient safety, we propose to take $\eta = 80\%$. However, we will also present the 95% credible interval for θ , as well as the entire posterior distribution for θ in a graphical fashion to the DSMC so that they have a full appreciation for the range of possible values of θ . All interim analyses will adjust for baseline level of encephalopathy, the stratification variable for this trial, whenever computationally feasible.

The choice of a prior distribution is essential and controversial in Bayesian analyses. Thus, we can compute the posterior probability of treatment harm and the posterior distribution of the associated relative risk under two sets of priors – (a) a non-informative prior that does not assume any substantive prior information about treatment differences in terms of the adverse events listed above, and (b) an informative prior based on treatment differences for these adverse events observed in the Phase I trial. However, we realize that the standard Bayesian approach of running the analysis with different priors provides only a partial solution, as the results on stopping are often inconclusive, especially when few data have accumulated. Instead of worrying about the selection of a single correct prior, we will also explore the use of a robust Bayesian approach which replaces a prior distribution with a class of priors and calculates the corresponding posterior probabilities for decision making²⁶.

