13.5. INTERIM MONITORING FOR EFFICACY OUTCOME

The relatively rare condition that this trial addresses means that it may take considerable time for this trial to enroll the requisite number of babies. Thus, even though the primary outcome is only available at 12 months corrected age, the enrollment period for the trial may make some interim efficacy data on the primary outcome available for monitoring by the DSMC. Note that because of the Bayesian nature of the trial design, interim efficacy looks at the data will not have any adverse Type I error consequences that are normally the case for a conventionally designed (or, ‘frequentist’) trial.

We propose to conduct one formal interim analysis of the accruing primary outcome data, examining both efficacy and futility, at a third of primary outcome accrual for this trial, provided that recruitment and intervention have not been completed by that point in time. The analysis for both efficacy and futility will adjust for baseline level of encephalopathy, the stratification variable for this trial, if computationally feasible

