13.7. INTERIM ESTIMATION OF TREATMENT FUTILITY

In addition to providing estimates of interim treatment efficacy, we will also conduct interim futility analyses for treatment efficacy. For this purpose, at each interim safety look, we will use the available data to calculate the posterior probability of concluding that the probability of survival free of cognitive impairment in the cord blood group would be higher than in the placebo group (i.e., the mean posterior RR for treatment benefit is greater than 1.0), if the trial continued until 120 patients were randomized and had their primary outcomes evaluated. In order to provide a more conservative basis for this estimate, and also to convince even those who strongly believed in this intervention at the outset, we will primarily use an optimistic prior for this calculation, with the prior belief set at a level of treatment benefit observed in the Phase I trial. However, in order to provide a broad overview and to explore the robustness of this estimate with respect to prior assumptions, this probability will also be calculated and presented for the two other prior distributions (skeptical and uninformative).

The DSMC may consider proposing termination of the trial for futility if this posterior probability of observing any treatment benefit, if the trial continued to full primary outcome accrual, is less than 10%.

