15.3. STATISTICAL ANALYSIS PLAN

All statistical analyses, including interim monitoring, will be conducted using the intent to treat principle, unless explicitly specified otherwise for certain secondary and/or post-hoc analyses. A Bayesian approach will be used for conducting the primary analysis in this trial. We propose to apply a log-binomial regression model and a neutral prior that will be centered at RR=1.0 to final

A Phase II Multi-site Study of Autologous Cord Blood Cells for Hypoxic Ischemic Encephalopathy (HIE) IND 14753 (BABYBAC II)

efficacy and safety data, where final data is defined as data contained in the study database after database lock. Database lock will occur either after 160 infants have completed the study or the study is terminated early for efficacy, futility, or safety. In addition to using a neutral prior, final analyses on locked data and some interim analyses will develop posterior distributions using skeptical (centered at $RR = 1.1$) priors and/or enthusiastic (centered at $RR = 0.625$) priors as well. In all analyses, MCMC methods will be used to sample from the Posterior distribution.

All analyses will involve estimating a Posterior distribution based on a log-binomial regression model with covariates and MCMC methods. In addition to estimating the treatment effect on the log relative risk scale, the log-binomial regression will adjust for level of encephalopathy. For the intercept and the encephalopathy terms, Normal (mean = 0, sd=100) priors will be used. For the term representing the log relative risk, skeptical, neutral, and enthusiastic priors will be used to estimate posterior distributions for the relative risk.

With respect to the primary efficacy endpoint, the estimated Posterior distribution of relative risk based on the data and the neutral prior will be used to determine posterior probabilities of >0 , >10 and $>20\%$ decrease in death or moderate/severe disability, as well as graphical displays of the Posterior distribution and appropriate 95% credible intervals for the relative risk. In addition to adjusting for level of encephalopathy and center in the log-binomial model, the final analysis of efficacy will also perform sensitivity analyses concerning possible treatment effect confounders present at randomization. All additional covariates added to the model will utilize Normal (mean=0, sd=100) priors.

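### The futility rule in 13.7 projects to 120 infants although 15.3 locks the database after 160, and 13.5 and 13.7 give different futility look schedules; the effect on the 10% rule is small

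*Combined protocol and SAP*

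**What the plan says.** Three parts of the combined protocol and SAP bear on the futility rule.

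- **Horizon in 13.7.** The probability of concluding benefit is calculated "if the trial continued until 120 patients were randomized and had their primary outcomes evaluated". The next paragraph lets the DSMC consider proposing termination when that same probability, "if the trial continued to full primary outcome accrual, is less than 10" per cent.
- **Trial size in 15.3.** "Database lock will occur either after 160 infants have completed the study", or on early termination for efficacy, futility or safety. Sections 2, 6 and 6.2 give the size as up to 160, and 15.2 anticipates 120 to 160.
- **Timing.** Section 13.7 states: "For this purpose, at each interim safety look, we will use the available data". Section 13.4 sets the safety looks "after every 40 babies enrolled in the trial have spent 24 hours post their final study transfusion". Section 13.5 instead proposes one formal interim analysis "at a third of primary outcome accrual for this trial, provided that recruitment and intervention have not been completed by that point in time", covering both efficacy and futility.

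Futility is judged mainly under the optimistic prior. Section 13.6 centres its enthusiastic prior at a relative risk of 0.625, but no section gives the spread of any prior.

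**The concern.** A predictive futility probability has meaning only for a stated final sample size. Section 13.7 gives two descriptions of that size, 120 infants and full accrual, and under 15.3 these are not the same number. Whoever programmes the calculation must choose between them. The shorter horizon leaves fewer future outcomes to reverse a poor interim result, so near the threshold it gives a lower probability of final benefit, and the DSMC would see a figure that does not describe the trial it is asked to judge.

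The programmer must also choose when to run the calculation, because 13.5 and 13.7 prescribe different looks. A rule that can end a trial should leave neither choice open.

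**Working it through.** **The plan's own figure.** The power table in 15.2 takes a control adverse-outcome rate of 0.6. Exact binomial power for a 95% interval excluding 1, and average posterior interval widths under Beta(0.5, 0.5) priors, are:

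| Cell-arm rate | Stated power / width | 60 per arm | 80 per arm |
|---|---|---|---|
| 0.30 | 0.92 / 0.45 | 0.92 / 0.450 | 0.97 / 0.385 |
| 0.35 | 0.81 / 0.48 | 0.80 / 0.483 | 0.89 / 0.418 |
| 0.40 | 0.62 / 0.51 | 0.61 / 0.511 | 0.72 / 0.442 |
| 0.45 | 0.38 / 0.54 | 0.39 / 0.540 | 0.47 / 0.463 |

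The four rows match 60 per arm (120 in total), not 80. The last row of the plan's table is not matched: type I error comes out at 0.050 to 0.051 against about 0.056, and the width at 0.59 to 0.62 against 0.54. So 120 is the size behind the power rows, and 160 is the size at lock. The difference is 160 − 120 = 40 infants.

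**Effect on the futility probability.** Inputs are the control rate 0.6 (15.2), the prior centre 0.625 (13.6), and 53 outcomes, a third of 160 (13.5, 15.3). The assumptions are a prior SD of 0.35 to 1.0, equal arms, a normal approximation on the log relative risk of death or a Bayley score below 85 (benefit is a value below 1), and no stratum adjustment.

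Let M and V_now be the interim posterior mean and variance, and V_final the posterior variance at the horizon. The probability that the final posterior mean favours cells is Φ(−M / √(V_now − V_final)).

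For an interim relative risk of 1.3 (rates 0.60 and 0.78) and SD 0.5:

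- Variance for one infant per arm: 0.4/0.6 + 0.22/0.78 = 0.9487.
- Data precision: 26.5/0.9487 = 27.93. Prior precision: 1/0.25 = 4. V_now = 1/31.93 = 0.0313.
- M = (4 × ln 0.625 + 27.93 × ln 1.3)/31.93 = 0.1706.
- To 120: 67 more outcomes add precision 33.5/0.9487 = 35.31, so V_final = 1/67.24 = 0.0149. The result is Φ(−0.1706/0.1282) = **9.2%**.
- To 160: 107 more outcomes add precision 53.5/0.9487 = 56.39, so V_final = 1/88.32 = 0.0113. The result is Φ(−0.1706/0.1414) = **11.4%**.

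| Assumed prior SD | To 120 (RR 1.3) | To 160 (RR 1.3) | Value at 160 when 120 gives exactly 10% |
|---|---|---|---|
| 0.35 | 20.4% | 22.8% | 12.4% |
| 0.5 | 9.2% | 11.4% | 12.2% |
| 1.0 | 4.3% | 5.8% | 12.1% |

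At SD 0.5 the triggering relative risk moves from 1.29 to 1.31, and at SD 1.0 from 1.23 to 1.25. With 40 outcomes (a third of 120), 10% at the shorter horizon becomes 11.4% to 11.6%. With a tight prior (SD 0.2) centred at 0.625, neither horizon reaches the threshold for any observed relative risk from 0.8 to 1.6.

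**How often decisions would differ.** A beta-binomial enumeration with flat Beta(1, 1) priors gives the chance that one horizon crosses 10% and the other does not. With no true effect it is 1.9% at 40 outcomes and 0.4% at 54. With true rates of 0.6 against 0.45, or 0.6 against 0.375, it is at most 0.1%.

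**Outcomes at the safety looks.** "We project accrual of 60-80 subjects per year" (section 6), and outcomes come at 12 to 16 months (8.5.6). With uniform accrual and no losses, outcomes available = enrolled − annual rate × follow-up/12, with a floor of zero.

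| Enrolled | 60/yr, 12 mo | 60/yr, 16 mo | 80/yr, 12 mo | 80/yr, 16 mo |
|---|---|---|---|---|
| 40 | 0 | 0 | 0 | 0 |
| 80 | 20 | 0 | 0 | 0 |
| 120 | 60 | 40 | 40 | 13 |

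The schedule in 13.7 therefore calls for a futility calculation with no outcomes at the first look and 0 to 20 at the second. Only the third, with 13 to 60, carries appreciable data.

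**The case against.** The strongest defence is that 120 is not arbitrary. It is the low end of the range anticipated in 15.2 and the size that reproduces the power rows, and 160 is worded as a maximum. That stands as an explanation of where the number probably comes from. It does not settle the matter, because 15.3 provides no lock at 120 short of an early stop, and 13.7 itself speaks of full accrual.

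The second defence is size. The wording is advisory, results under all three priors go to the DSMC, and the shift is about 2 points. That also stands. In the worked example only the assumed SD of 0.5 puts the two horizons on opposite sides of 10%. At 0.35 neither signals futility, and at 1.0 both do.

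Two stronger readings are tempting, and the documents do not support them.

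- A reader might infer that about 120 or more infants will already be randomised at the look, so the projection is empty. For the one-third look in 13.5, the number randomised would be 113 to 160 (53 outcomes plus 60 to 107 enrolled during follow-up), or 100 to 147 if a third means 40 of 120. But 13.7 places futility at the safety looks, where 40 and then 80 are enrolled at the first two. The clause also requires outcomes to be evaluated: with 53 known, 67 of 120 are still to come.
- A reader might infer a larger gap from a look with many more outcomes. On the projected accrual, no safety look before 160 enrolled has more than 60 outcomes, and at 160 recruitment is ending.

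**Conclusion.** The inconsistency is in the text and needs no assumption: 13.7 projects to 120, describes that horizon as full accrual, and 15.3 completes at 160. The conflict between 13.5 and 13.7 over when futility is assessed is equally plain.

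The numerical consequence is small. A probability of 10% at 120 corresponds to about 12% at 160 with 53 outcomes, for a 0.625-centred prior with SD 0.35 to 1.0, and the two horizons would rarely lead to different signals. These sizes depend on a prior spread that the documents do not give, on the normal approximation, and on uniform accrual without loss to follow-up. The disagreement rates use flat priors, not the optimistic prior. The figures do not show that the rule would often stop the trial wrongly.

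Severity: a minor consistency correction to a stopping rule.

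**What to change.** In 13.7, replace the 120-patient horizon with the size at which 15.3 locks the database: 160, or the enrolment target in force at the look. The threshold paragraph then refers to the same quantity as the calculation.

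Reconcile 13.5 and 13.7 to one futility look schedule. If the one-third look is kept, state the number of outcomes it means (53 of 160). If the safety looks are kept, state what is reported when few or no outcomes are available.

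The cost is one number and a sentence or two. The downside is that the futility trigger becomes slightly harder to reach.

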14. DATA SAFETY MONITORING COMMITTEE

A DSMC will be responsible for monitoring the safety of the trial. The DSMC will have a minimum of three members including a biostatistician, a neonatologist, and an expert in cord blood stem cell transplant. The DSMC members will be independent from any enrolling center and guided by a DSMC charter.

A Phase II Multi-site Study of Autologous Cord Blood Cells for Hypoxic Ischemic Encephalopathy (HIE) IND 14753 (BABYBAC II)

15. STATISTICAL CONSIDERATION

15.1. STUDY DESIGN

This study is a prospective Phase II prospective, randomized, double-blind, placebo controlled, multi-center trial designed to assess the safety and efficacy of two infusions of autologous UCB cells or placebo in newborns born in distress.

15.2. ESTIMATES OF AVAILABLE AND REQUIRED SAMPLE SIZE

In our phase I study to date, 16 of 25 (64%) cell recipients with known one year outcomes have survived with all three Bayley III assessments (Cognitive, Motor, and Language) ≥ 85 , and 25 of 63 (40%) of the cooled-only infants with known one year outcomes has survived with all three Bayley III domain scores ≥ 85 . (13) We acknowledge the limitations of a one year Bayley score, but would note that our rate of survival with Bayley scores ≥ 85 among cooled-only infants is consistent with the previously reported Whole Body Hypothermia studies rates of survival at 12–24 months without moderate or severe impairment (1 -4).

For the phase II study, rather basing the sample size on effect size, we would propose a Bayesian approach as used in the NRN Late Hypothermia study. Because this is phase II where our aim is to detect a trend favoring cell recipients, and to accumulate data that will inform design and sample size calculations for a phase III study of efficacy, we anticipate that two years of enrollment would provide approximately 120-160 infants, 60-80 in each group.

Control	Cell Recipients	95% Confidence Interval	Power
0.6	0.30	0.45	0.92
0.6	0.35	0.48	0.81
0.6	0.40	0.51	0.62
0.6	0.45	0.54	0.38
0.6	0.60	0.54	0.056

The Bayesian analysis will permit calculation of a probability of treatment benefit. Within the range of an active group proportion of 0.3 to 0.45, the average 95% credible interval width ranges from 0.45 to 0.54 when the control group has a proportion having the primary outcome (death or Bayley III scores < 85) of 0.6. If the decision rule for declaring a win is the posterior 95% credible interval must exclude 1, then the design has power ranging from 0.92 to 0.38 with a Type 1 error of about 0.056.

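### Does the power table in section 15.2 need recalculating because it names no N or prior SD and repeats the width 0.54 in its null row?

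*Combined protocol and SAP*

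**What the plan says.** Section 15.2 does not derive the sample size from a target effect. It gives a recruitment forecast: "we anticipate that two years of enrollment would provide approximately 120-160 infants, 60-80 in each group". The table that follows sets a control rate of 0.60 for death or a Bayley III score below 85 against cell-arm rates of 0.30, 0.35, 0.40, 0.45 and 0.60. One column is headed as a 95% confidence interval and reads 0.45, 0.48, 0.51, 0.54 and 0.54. The power column reads 0.92, 0.81, 0.62, 0.38 and 0.056. The paragraph below explains the first of these columns: "Within the range of an active group proportion of 0.3 to 0.45, the average 95% credible interval width ranges from 0.45 to 0.54". A win is declared when the 95% credible interval excludes 1, so the scale is the relative risk. Under that rule, the section says, "then the design has power ranging from 0.92 to 0.38 with a Type 1 error of about 0.056".

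Two totals appear elsewhere. The futility projection in section 13.7 asks what would be concluded "if the trial continued until 120 patients were randomized and had their primary outcomes evaluated". Section 15.3 says "Database lock will occur either after 160 infants have completed the study", unless the trial stops early.

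For the final model, section 15.3 specifies "a neutral prior that will be centered at RR=1.0" and gives no SD for that term. It does give one for the nuisance terms: "For the intercept and the encephalopathy terms, Normal (mean = 0, sd=100) priors will be used". It also states that "the log-binomial regression will adjust for level of encephalopathy".

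**The concern.** Power depends on N and on the spread of the treatment prior, and neither is attached to the table. A reader cannot tell whether the figures describe 120 or 160 infants.

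The null row also looks wrong. With the control rate fixed, the width on the relative-risk scale rises by 0.03 at each step through the first four rows. It then stays at 0.54 when the cell rate goes from 0.45 to 0.60. In a plain two-proportion calculation the null row must be wider, so the figure might have been copied from the row above or computed at another N.

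This table is the plan's only numerical account of how the design performs. If it were wrong in a way that overstated power, the case for 120 to 160 infants would weaken.

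**Working it through.** **Inputs.** From 15.2: control rate 0.60, cell rates 0.30 to 0.60, and a win when the 95% interval for the RR excludes 1. Assumed: equal arms, complete outcomes, flat prior on log RR.

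**1. Reproduce the table with an unadjusted model.** With n per arm,

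SE² = (1 − pC)/(n·pC) + (1 − pT)/(n·pT), width = 2·RR·sinh(1.96·SE).

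At n = 60:
- 0.45 row: SE² = 0.4/36 + 0.55/27 = 0.03148, SE = 0.1774, width = 2 × 0.75 × sinh(0.3478) = 0.532.
- Null row: SE² = 2 × 0.4/36 = 0.02222, SE = 0.1491, width = 2 × sinh(0.2922) = 0.593.

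Averaging over all binomial outcomes instead of plugging in expected counts gives (width / power):

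| Cell rate | Plan | 60 per arm | 80 per arm |
|---|---|---|---|
| 0.30 | 0.45 / 0.92 | 0.458 / 0.924 | 0.392 / 0.971 |
| 0.35 | 0.48 / 0.81 | 0.489 / 0.803 | 0.419 / 0.889 |
| 0.40 | 0.51 / 0.62 | 0.517 / 0.612 | 0.443 / 0.715 |
| 0.45 | 0.54 / 0.38 | 0.542 / 0.393 | 0.465 / 0.470 |
| 0.60 | 0.54 / 0.056 | 0.606 / 0.050 | 0.520 / 0.046 |

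The first four rows agree with 60 per arm, the bottom of the stated range and the 120 of section 13.7.

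**2. The null row in that model.** The ratio to the row above is 0.606/0.542 = 1.118. Two values that both round to 0.54 allow at most 0.545/0.535 = 1.019. A Normal prior on log RR with an assumed SD of 0.5 or 0.35 lowers the ratio only to about 1.10 or 1.09. A null width of 0.54 needs about 75 per arm, where the 0.45 row would be 0.48. In an unadjusted model, then, the fifth width does not belong with the other four.

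**3. The planned model adjusts for encephalopathy.** With a separate baseline in each stratum, information on the common log RR is the sum of 1/v over strata, where v is the SE² above computed within the stratum. The documents give no severity mix, so these are assumptions that keep the overall control rate at 0.60.

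*54 per arm, 25% severe with event rate 0.85.* The moderate rate is (0.60 − 0.25 × 0.85)/0.75 = 0.517; stratum sizes are 13.5 and 40.5.
- Null row: v = 0.0261 (severe) and 0.0462 (moderate); information 38.25 + 21.65 = 59.90; SE = 0.1292; width 2 × sinh(0.2533) = 0.512.
- 0.45 row (RR 0.75): v = 0.0552 and 0.0621; information 18.12 + 16.10 = 34.21; SE = 0.1710; width 1.5 × sinh(0.3351) = 0.512.

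The ratio is 1.00. A severe stratum with a high event rate is most informative when the treatment does nothing, and that narrows the null interval.

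*60 per arm, 25% severe with event rate 0.75.* The moderate rate is (0.60 − 0.25 × 0.75)/0.75 = 0.55; stratum sizes are 15 and 45.
- Null row: information 22.5 + 27.5 = 50.0; width 0.562.
- 0.45 row: information 13.5 + 20.07 = 33.57; width 0.517.

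The ratio is 1.09, so the answer depends on the mix.

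**4. Full posterior simulation of the adjusted model.** The plug-in figures ignore small-sample spread. Simulating the posterior (flat log-RR prior, probabilities capped at 1) gives ratios of about:
- 1.05 to 1.07 for 54 per arm, 25% severe at 0.85;
- 1.03 for 52 per arm, 25% severe at 0.90;
- 0.98 to 0.99 for 60 per arm, 20% severe at 0.95.

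In one run of the first mix, widths were 0.455/0.484/0.508/0.524 with null 0.558, and power was 0.924/0.818/0.631/0.410. All five widths lie within 0.018 of the plan's. Across prior SDs and N, the unadjusted model came no closer than 0.024 on all five.

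**5. Type I error.** The unadjusted calculation gives 0.047 to 0.050 at 60 per arm, against 0.056. If the plan used about 1,000 simulated trials (an assumption), the standard error is √(0.05 × 0.95/1000) = 0.007, so the gap is within noise.

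**The case for a change.** The best case for a correction is that the unadjusted model at 60 per arm fits the first four rows almost exactly and misses only the fifth width. A value copied from the row above explains that simply. The adjusted model fits the first four rows less closely, and its null rejection rate in the 54-per-arm example is about 0.03, further from 0.056. It also closes the gap only when the severe stratum has a high event rate. A reader should not have to work N out backwards, and the column heading is wrong as it stands.

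Much of this is fair. A clerical slip in the null row is plausible. The table should have carried its N, and the heading is loose, although the paragraph below says what the numbers are. The missing SD for the treatment prior is a real gap, but it concerns how the prior is specified in sections 13.6 and 15.3, not the arithmetic here.

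Two claims do not stand. It is not shown that 0.54 cannot share an N with the other rows, because the planned model can bring the two widths close together. Nor should the unadjusted 0.61 (60 per arm) or 0.52 (80 per arm) replace the printed value, since neither comes from the model the trial will fit. The inferred 60 per arm has the same weakness: adjusted calculations give similar rows at 52 to 54.

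**Conclusion.** No change to the plan follows. What remains is missing labelling, a loose column heading that the text explains, and one width that may be a slip.

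The null-row width enters no decision rule and no sample-size argument; the text's own statement about widths stops at a cell rate of 0.45. The power figures, which do matter, are attainable within the stated 60-80 per group. If 160 infants complete, they err on the cautious side in the unadjusted calculation. With a flat prior, power at 80 per arm is 0.971/0.889/0.715/0.470 against the stated 0.92/0.81/0.62/0.38, higher by 0.05 to 0.10. With an assumed prior SD of 0.35 it is 0.944/0.828/0.632/0.394, higher by 0.01 to 0.02. Widths there are smaller than stated by about 0.05 to 0.10.

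This rests on about 60 analysed infants per arm, or slightly fewer if adjustment helps as in the assumed mixes. If enrolment ended at 120 and outcomes were then lost, power could fall below the table. That would be a matter of recruitment and follow-up, and relabelling the table would not alter it. Section 15.2 presents the size as what two years of enrolment should yield in a phase II trial looking for a trend, so a corrected null width would leave N, the decision rule and the analysis where they are.
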